9.6.1 SUB-GROUP ANALYSES

9.6.1.1 PRIMARY ENDPOINT

The target population for the HepQuant SHUNT Test will include adults, age 18 or higher, both men and women, all races or ethnicities, and all etiologies of CLD. The Test measures the flow-dependent clearance of cholate from both systemic and portal circulations – measurements that are related to the common pathophysiology of progression of all liver disease. Because the pathophysiology is similar across age, gender, and race or ethnicity, we do not anticipate any differences in the relationship of DSI cutoff to likelihood for large esophageal varices related to these variables.

There could be differences in the relationship of DSI cutoff to likelihood for large esophageal varices related to the etiology of liver disease. Liver diseases, especially at earliest stages differ in the lobular target or locus of the necroinflammatory and fibrotic process, i.e., periportal (zone 1), sinusoidal or transitional (zone 2), or pericentral (zone 3). Although necro-inflammation overlaps between zones for all liver diseases, the primary target for cholestatic liver disease is zone 1, viral liver diseases zones 1 and 2, NASH zone 2, and alcohol zone 3. With progression to end-stage decompensated cirrhosis these distinctions disappear.

Performance of the DSI test (NLR, FPR, sensitivity and specificity) will be reported separately in subgroups defined by age, sex, race, and disease etiology. These results will be presented as forest plots in order to identify any subgroups in which DSI test performance differs from the overall performance.

9.6.1.2 SECONDARY ENDPOINTS

Secondary efficacy endpoint (Probability and Calibration Curves): Regression analyses will be performed for DSI versus probability of large varices for individual etiologies of disease with over 50 subjects and for the categories of cholestatic and non-cholestatic liver diseases.

9.6.1.3 TABULATION OF INDIVIDUAL PARTICIPANT DATA

Individual participant data will not be listed.

9.6.2 EXPLORATORY ANALYSES

Exploratory 1 (AUROC of DSI for large esophageal varices): The c-statistic for the AUROC for DSI in likelihood of large esophageal varices will be compared to the c-statistic for the AUROC of LSM plus platelet count in likelihood of large esophageal varices. The most complete study with publication of AUROCs for LSM plus platelet count is from Abraldes, et al (8) where the AUROC was 0.76 for varices needing treatment (large varices or small varices with red signs). Given this benchmark the performance goal is an AUROC \geq 0.76 for DSI in likelihood of large esophageal varices.

In addition, we will examine the diagnostic performance (sensitivity, specificity, PPV, NPV, NLR, PLR, FNR, miss rate⁸) of DSI over the full range of DSI to define the Optimal DSI for "Rule Out" – highest sensitivity and NPV with lowest FNR. We will also compare the diagnostic performance of this "optimum" DSI to DSI 18.3. The purpose of this analysis is to provide upside and downside performance of DSI around the validated cutoff of DSI 18.3.

This analysis will yield a table of sensitivities, specificities, NPVs, PPVs, NLRs, PLRs, FNRs, and miss rates⁸ over the given range of DSI that could be included in a package insert to help the clinician interpret a given DSI result.

AUROCs of DSI in likelihood of large varices will be constructed for individual etiologies of disease with over 100 subjects and for the categories of cholestatic and non-cholestatic liver diseases.

Exploratory 2 (DSI for Small or Any Size of Esophageal Varices). The analyses listed above for primary objective, secondary objective 1, and secondary objective 2 will be repeated using small varices in one set of analyses and any size of varices in another set of analyses.

Exploratory 3 (STAT). The serum concentration of d4-cholate from the 60-minute time point (STAT) of the HepQuant SHUNT test correlates well with DSI (r^2 =0.88). The STAT value represents a simplified, single point version of DSI. For this reason, we propose to evaluate the diagnostic performance of a cutoff for STAT defined from the HALT-C Training dataset for large esophageal varices and esophageal varices of any size.

The NLR performance goals for the STAT cutoff applied to the CLD Validation dataset are identical to the goals explained above for DSI: that the upper limit of the 95% Confidence Interval for NLR rules out NLR > 0.52. The sample size considerations with DSI for the primary efficacy endpoint and secondary efficacy endpoint 1 are also applicable STAT – the same limits for sensitivity and specificity. We will include age, gender, race, and ethnicity in multi-variable logistic regression of the association of STAT with large esophageal varices.

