¹ NOTE: There is some disagreement in the literature regarding the calculation of the False Negative Rate (FNR) for a test. FNR has been defined by the U.S. Food and Drug Administration in a disease-centric manner as 1 - Sensitivity ((Σ False negative) / (Σ Condition positive)), while being defined in much of the clinical literature in a test-centric manner as 1- NPV ((Σ False negative) / (Σ Predicted condition negative)). To compare to published results from the literature, in this protocol, the test-centric definition for FNR (1-NPV) has been used, and the term "miss rate" has been used to express 1-Sensitivity.

population is 20%. Each subject will have been selected to undergo a future EGD for variceal screening or surveillance according to standard criteria used in current clinical practice.

Enrolled subjects will undergo standard clinical assessment, laboratory tests, and the HepQuant SHUNT Test. The previously scheduled EGD will be performed no more than 6 weeks following the HepQuant SHUNT Test.

The relationship of DSI to large varices will be analyzed by AUROC and the diagnostic performance of the DSI cutoff \leq 18.3 will be defined by sensitivity, specificity, PPV, NPV, NLR, PLR, FNR and miss rate². The validated DSI cutoff will aid the clinician in the decision to proceed with or avoid the EGD.

Objectives:

The **primary objective** of this study is to validate DSI ≤18.3 for identifying subjects with CLD selected for future EGD for variceal screening or surveillance who are not likely to have large esophageal varices if the EGD were to be performed ("Rule Out").

The Secondary objective is to define the relationship of DSI to probability for large varices over the full range of DSI.

Exploratory objective 1 is to examine the diagnostic performance of DSI for large varices over the full range of DSI. We will generate and evaluate the AUROC (c-statistic) for DSI in likelihood of large esophageal varices. The AUROC for DSI in likelihood of large varices will be compared to the c-statistic 0.76 reported by Abrades, et al, for LSM plus platelet count (8).

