There may be additional advantages of the HepQuant SHUNT test. The test is done once, while TE is recommended to be done at least twice on two separate days. Both tests require fasting. The NLR of 0.09 for DSI \leq 18.3, compared to published NLRs, suggests that the DSI cutoff may be more accurate in negative likelihood of large esophageal varices compared with the current practice using LSM with or without platelet count.

High Risk Patients defined by Cirrhosis or Advanced CLD

In the ANTICIPATE Study (29) liver stiffness, platelet count, and spleen diameter were evaluated in 518 patients with CLD from five centers in Europe and Canada. Liver stiffness measurement [LSM] by transient elastography [TE], platelet count, and spleen diameter (with calculation of liver stiffness to spleen/platelet score [LSPS] score and platelet-spleen ratio [PSR]) were compared in their ability to predict risk of large esophageal varices ("varices needing treatment, VNT"). The AUROCs were 0.67 for TE alone, 0.73 for TE plus platelet count, 0.74 for PSR, and 0.79 for LSPS.

Furthermore, a diagnosis of cirrhosis, whether by biopsy or noninvasive means, does not provide an unequivocal link to varices or need for endoscopy. Many patients with cirrhosis lack clinically significant portal hypertension and do not have varices. Care providers don't necessarily link cirrhosis, per se, to need for endoscopy. The latter is exemplified by a study of 4230 veterans with HCV cirrhosis with median followup of 6.1 years. Only 33.8% of patients meeting AASLD or Bueno VI guidelines had an EGD performed for variceal screening (77). Diagnosis of cirrhosis fails to trigger care providers to refer patients for endoscopic variceal screening.

The HepQuant SHUNT Approach. The HALT-C Training Dataset defined an AUROC 0.82 for DSI in likelihood of Large Esophageal Varices. This compares favorably with AUROCs measured in the Anticipate Study – ranging from 0.67 for TE alone, to 0.79 for LSPS. The performance of HepQuant SHUNT and DSI for likelihood of Large Esophageal Varices is due to the fact that the HepQuant SHUNT test directly measures portal-systemic shunting, linking it directly to variceal pathophysiology. As such, a HepQuant SHUNT test result may provide a more direct link to varices resulting in an appropriate referral for endoscopy.

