New varices are unlikely to develop, and small varices are unlikely to become large within 6 weeks. The rate of developing new varices in a cirrhotic patient without varices is approximately 3 to 5%/year (63,64). The rate of small varices enlarging to become large varices is approximately 12-15%/year (64-69). Over 6 weeks these rates would be 0.6% and 1.8%, respectively. Given these slow rates of variceal progression, we conclude that the EGD findings are not expected to change significantly within the 6-week window. Note that the average time interval between the SHUNT test and EGD is likely to be far less than 6 weeks.

The following EGD findings will be recorded:

- Esophageal varices
 - Present or absent; to be categorized as present the varices must protrude into the esophageal lumen during insufflation of the esophagus
 - If varices are present, record size as small (<5 mm diameter, or Grade 1) versus large (5 mm or more in diameter, or Grades 2 or 3)
 - If varices are present, record presence or absence of red wale marks, and whether they are mild, moderate, or severe
- Gastric varices
 - Present or absent
 - If gastric varices are present, record size as small (<5 mm diameter, or Grade 1) versus large (5 mm or more in diameter, or Grades 2 or 3)
 - If gastric varices are present, record presence or absence of red wale marks, and whether they are mild, moderate, or severe
- Portal hypertensive gastropathy
 - o Present or absent
 - o If present, record whether it is mild, moderate or severe

The primary endoscopic endpoint is large esophageal varices. We will also record and report the endoscopic findings of red wale marks, gastric varices, and portal hypertensive gastropathy, but are not planning any formal analysis of these features as endpoints. Red wale marks may amplify risk for variceal hemorrhage in those with esophageal varices – for this reason we will examine the relationship of DSI to red wale marks.

To ensure consistency across centers, all EGDs will be performed by endoscopists experienced in the evaluation and treatment of esophageal varices. The endoscopists will be identified and designated by the clinical center's PI.

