DSI ≤18.3 lowers the Miss Rate for Large Varices. Miss rate for large varices is defined by the number of cases with large varices below cutoff divided by the total number of cases with large varices. For the HALT-C Training dataset the Miss Rate was 1/22 = 4.5%. For the pooled results from the 10 published studies of LSM plus platelet count the Miss Rate was 21/319 = 6.6%. For individual published studies of LSM plus platelet count, the Miss Rate ranged from 0.0 to 18.2%.

In addition, the AUROC for DSI in likelihood of large varices was c-statistic = 0.82 which compares favorably to cstatistic = 0.76 for LSM plus platelet count, i.e., an improvement in overall diagnostic performance.

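### The exploratory AUROC goal of 0.76 is not reconciled with the 0.73 quoted from the same publication, and its benchmark endpoint is broader than the trial's

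*Combined protocol and SAP*

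**What the plan says.** Section 9.6.2 (Exploratory 1) compares the DSI c-statistic for large esophageal varices with a published value for liver stiffness plus platelet count. It says that in reference 8 "the AUROC was 0.76 for varices needing treatment (large varices or small varices with red signs", and continues: "Given this benchmark the performance goal is an AUROC" of at least 0.76, for large esophageal varices. It attaches no confidence limit or test to that goal.

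The synopsis (1.1) uses the same comparator, also from reference 8: the DSI AUROC "will be compared to the c-statistic 0.76 reported by" that publication. Section 9.5 repeats the number without a citation, setting the training c-statistic of 0.82 against "0.76 for LSM plus platelet count, i.e., an improvement in overall diagnostic performance".

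Section 2.2.4, describing the ANTICIPATE study under reference 29, reads: "The AUROCs were 0.67 for TE alone, 0.73 for TE plus platelet count, 0.74 for PSR, and 0.79 for LSPS". It ties those figures to large varices, labelled varices needing treatment.

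On the trial's own endpoint, 4.1.2 makes large esophageal varices the endoscopic endpoint, and 4.3.1 classes every other varix as small, with no exception for red signs. Section 4.1.2 records size and red wale marks and adds that "we will examine the relationship of DSI to red wale marks". Section 8.1 plans no formal analysis of red signs.

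**The concern.** A numeric performance goal taken from the literature should rest on one identifiable figure for a matching endpoint. Here the protocol attributes two figures for stiffness plus platelet count to one article. It builds the goal on one of them without saying how they differ. It also sets a goal for large varices only from a benchmark that, by its own description, counts some small varices as positive.

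What is at stake is the reading of exploratory objective 1. As written, the goal is judged on the point estimate, so a shift of 0.03 in the threshold can turn a miss into a pass. The improvement claimed in 9.5 also depends on the figure used: 0.82 − 0.76 = 0.06, or 0.82 − 0.73 = 0.09.

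**Working it through.** **Whether 0.76 can be reproduced.** It is a literature value. The documents give no data or formula behind it, so the check is a comparison of sections.

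**One source or two.** References 8 and 29 in section 11 carry the same title, journal, year, volume and pages (Hepatology 2016;64:2173-2184). The value for transient elastography alone is 0.67 both in 4.2.2.1 (citing reference 8) and in 2.2.4 (citing reference 29), which supports a single source.

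| Section | Reference | Marker | Endpoint as labelled | AUROC |
|---|---|---|---|---|
| 1.1 | 8 | stiffness + platelets | large varices | 0.76 |
| 9.5 | none | stiffness + platelets | large varices | 0.76 |
| 9.6.2 | 8 | stiffness + platelets | varices needing treatment, including small with red signs | 0.76 |
| 2.2.4 | 29 | elastography + platelets | large varices, labelled varices needing treatment | 0.73 |

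Sections 2.2.4 and 9.6.2 both use the label varices needing treatment, so the label alone does not explain the gap. A different model or analysis set might: 2.2.4 reports 518 patients for the study, while Table 1 lists 379 in the row for that publication.

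**How much 0.03 matters.** Inputs: 80 cases and 320 non-cases (9.2.1); 50 and 200 at an interim stop (20% of 250); training AUROC 0.82 (4.2.2.1). The standard error formula (Hanley-McNeil) and the normal approximation are assumptions of this review, since the plan names no method. For AUROC A, m cases and n non-cases:

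SE² = [A(1−A) + (m−1)(Q1−A²) + (n−1)(Q2−A²)] / (mn), where Q1 = A/(2−A) and Q2 = 2A²/(1+A).

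At A = 0.75, m = 80, n = 320:
- Q1 = 0.75/1.25 = 0.600 and Q2 = 1.125/1.75 = 0.6429.
- The numerator is 0.1875 + 79 × 0.0375 + 319 × 0.08036 = 28.78.
- SE = √(28.78/25,600) = 0.0335.
- P(estimate ≥ 0.73) = Φ(0.02/0.0335) = 72%.
- P(estimate ≥ 0.76) = 1 − Φ(0.01/0.0335) = 38%.

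| True AUROC | SE (80/320) | Meets 0.76 | Meets 0.73 |
|---|---|---|---|
| 0.73 | 0.0343 | 19% | 50% |
| 0.75 | 0.0335 | 38% | 72% |
| 0.76 | 0.0331 | 50% | 82% |
| 0.78 | 0.0322 | 73% | 94% |
| 0.80 | 0.0312 | 90% | 99% |
| 0.82 | 0.0301 | 98% | >99% |

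The gap is about 0.03/0.033 = 0.9 standard errors. At 50/200 the standard error at 0.75 is 0.0424, and the goal is met in 41% of trials (0.76) against 68% (0.73). At 0.82 the figures are 94% and 99%.

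**How firm 0.82 is.** It rests on 22 cases and 195 non-cases. The same formula gives SE 0.0561, so an approximate 95% interval is 0.82 ± 1.96 × 0.0561, or 0.71 to 0.93. That covers the whole range in which the choice of threshold matters.

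**Endpoint mismatch.** The documents do not say how many small varices with red signs to expect, or how DSI behaves in them. Neither the size nor the direction of the effect can be computed.

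**The case against.** The strongest defence is that the benchmark in use is consistent. Each section that sets a goal or makes the planned comparison (1.1, 9.5, 9.6.2) says 0.76; 0.73 appears only as background, and no goal is built on it. An analyst following 9.6.2 has a single threshold. That stands, but it does not tell the reader why the same article is credited with two values.

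A reader might infer that 0.76 is wrong, or that the figure was chosen to help the device. The documents support neither. They cannot show which value is right, and 0.76 is the harder threshold: if 0.73 were correct, DSI would be held to more than the comparator achieved.

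On the endpoint, 2.1.1 says large varices and varices needing treatment are used interchangeably. That convention does not close the gap, because 9.6.2 gives the benchmark a broader definition in the sentence before the goal. It is fair to add that the mismatch is therefore visible in the plan. It is also fair that 8.1 deliberately leaves red signs out of formal analysis and gives a guideline-based reason. An exact match cannot be assured: the trial grades red wale marks mild, moderate or severe (4.1.2), 8.1 singles out moderate to severe, and the source's threshold for red signs is not given.

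Finally, 9.4.1 and 9.5.1 call for 95% confidence intervals on measures of diagnostic accuracy, so uncertainty around a pass or miss should be visible.

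**Conclusion.** The concern holds as two limited points about an exploratory goal. The plan quotes 0.76 and 0.73 for the same marker pair from one article without reconciling them, and it compares a large-only AUROC with a benchmark on a broader endpoint.

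Under the Hanley-McNeil assumption and 20% prevalence, the 0.03 gap can change whether the goal is met if the true AUROC is about 0.73 to 0.80. It makes almost no difference if the training value of 0.82 carries over. The endpoint mismatch is real but unquantified.

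It would go too far to call the benchmark unreliable or to extend the point to the trial's main conclusion. Validation and interim stopping rest on NLR and sensitivity, so the primary criteria, type I error and sample size are unaffected. This is a worthwhile tidy-up of minor weight.

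**What to change.** - Check the figure in the source. Use one value in 1.1, 2.2.4, 9.5 and 9.6.2, stating the model, analysis set and endpoint it belongs to. If both values are genuine, say what distinguishes them and which one sets the goal.
- Merge references 8 and 29.
- Keep the large-only AUROC as the main exploratory result. For the benchmark comparison, add a DSI AUROC on the matching endpoint (large varices, or small varices with red wale marks). State in advance which red wale grades count, and note that the match is approximate because the source's threshold is not given.

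The cost is one source check, a text correction and one extra AUROC from size and red wale data that 4.1.2 already records. No new data are needed and no planned analysis is displaced.

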10 SUPPORTING DOCUMENTATION AND OPERATIONAL CONSIDERATIONS

⁸ In this protocol, FNR is defined as 1-NPV and miss rate is defined as 1-Sensitivity. See the footnote in Section 1.1 for a discussion of these two measures.

10.1 Regulatory, Ethical, and Study Oversight Considerations

10.1.1 INFORMED CONSENT PROCESS

In obtaining and documenting informed consent, the investigator must comply with applicable regulatory requirements (e.g., 45 CFR Part 46, 21 CFR Part 50, 21 CFR Part 56). Prior to the beginning of the trial, the investigator should have the IRB's written approval for the protocol and the written informed consent form(s) and any other written information to be provided to the participants.

10.1.1.1 CONSENT/ASSENT AND OTHER INFORMATIONAL DOCUMENTS PROVIDED TO PARTICIPANTS

Consent forms describing in detail the study intervention, study procedures, and risks are given to the participant and written documentation of informed consent is required prior to starting intervention/administering study intervention. The ICF for this study is in **Appendix F**.

10.1.1.2 CONSENT PROCEDURES AND DOCUMENTATION

The process of Informed Consent will be initiated prior to the individual's agreeing to participate in the study and will continue throughout the individual's study participation. Consent forms will be Institutional Review Board (IRB)-approved and the participant will be asked to read and review the document. The investigator will explain the research study to the participant and answer any questions that may arise.

A verbal explanation will be provided in terms suited to the participant's comprehension of the purposes, procedures, and potential risks of the study and of their rights as research participants. Participants will have the opportunity to carefully review the written consent form and ask questions prior to signing. The participants should have the opportunity to discuss the study with their family or surrogates or think about it prior to agreeing to participate.

The participant will sign the informed consent document prior to any procedures being done specifically for the study. Participants must be informed that participation is voluntary and that they may withdraw from the study at any time, without prejudice. A copy of the informed consent document will be given to the participants for their records.

The informed consent process will be conducted and documented in the source document (including the date), and the form signed, before the participant undergoes any study-specific procedures. The rights and welfare of the participants will be protected by emphasizing to them that the quality of their medical care will not be adversely affected if they decline to participate in this study.

10.1.2 STUDY DISCONTINUATION AND CLOSURE

This study may be suspended or prematurely terminated if there is sufficient reasonable cause. Written notification, documenting the reason for study suspension or termination, will be provided by the suspending or terminating party to the study participants, investigators, Investigational Device Exemption (IDE) Sponsor and regulatory authorities. If the study is prematurely terminated or suspended, the Principal Investigator (PI) will promptly inform study participants, the Institutional Review Board (IRB), and sponsor and will provide the reason(s) for the termination or suspension. Study participants will be contacted, as applicable, and be informed of changes to study visit schedule.

Circumstances that may warrant termination or suspension include, but are not limited to:

- Determination of unexpected, significant, or unacceptable risk to participants
- Demonstration of efficacy that would warrant stopping

- Insufficient compliance to protocol requirements
- Data that are not sufficiently complete and/or evaluable
- Determination that the primary endpoint has been met
- Determination of futility

Study may resume once concerns about safety, protocol compliance, and data quality are addressed, and satisfy the sponsor, IRB and/or Food and Drug Administration (FDA).

